6.7.2 Adverse Events

All AEs recorded on the CRF will be coded using the MedDRA dictionary [Version 23.1 (or a later version if updated during the study)] and treatment – emergent AEs (TEAEs) are defined as follows:

- TEAEs are events with start date on or after the date and time of the first dose of treatment or events with start date prior to the date and time of the first dose of treatment whose severity worsens on or after the date and time of the first dose of treatment.

If an event where AE start/stop date is missing/partial, the following imputation rule will be applied:

Imputation rules for start date of AEs:

- If start date is completely missing, start date will be imputed to be the first dose date of study treatment;
- For a partial start date (day is missing, or day and month are both missing):
 - none missing part of the partial date < the first dose date: the last day of the month/year
 - none missing part of the partial date = the first dose date: the first dose date
 - none missing part of the partial date > the first dose date: the first day of the month/year

Imputation rules for end date of AEs:

CONFIDENTIAL

Page 24 of 30

Statistical Analysis Plan

Sponsor Name: Bridge Biotherapeutics, Inc.
Sponsor Protocol ID: BBT401-UC-005

- If end date is completely missing, then end date remains missing (assuming ongoing event);
- For a partial end date, the last day/month will be imputed. If only day is missing, the last day of the month will be imputed; if both day and month are missing, then the last day of the year will be imputed. If the imputed end date is after the end of study date, then imputed end date will be set as the end of study date.

If imputed AE start date is after the imputed AE stop date, then start date will be set to the imputed AE stop date.

Imputed dates will be used to determine whether an AE is treatment-emergent and will not be displayed in data listings.

All AE data will be listed. Treatment-emergence status will be flagged in the listing. In addition, corresponding listings of SAEs, AEs leading to discontinuation of treatment and AEs resulting in death will be produced.

Summary tables of TEAEs will be produced for each phase by treatment group for the Safety Population. AE starting date which is within the induction phase will be summarised under the induction phase. Similarly, an AE starting date which is within the extension phase will be summarised under the extension phase.

The severity of all AEs is recorded as mild, moderate, or severe. If severity is missing for a TEAE, it will be considered severe only in the overall category in the summary tables.

The relationship between an AE and treatment is assessed as not related, unlikely related, possible related, or related. A treatment-related AE is an AE considered by the investigator as possibly related, or related to treatment or with unknown/missing relationship to treatment.

An overview table will summarize the number and percentage of subjects with at least one of the following TEAEs, where subjects with more than one TEAE in a particular category are counted only once in that category:

- Any TEAE;
- Treatment-Related TEAE;
- TEAE Leading to Treatment Discontinuation;
- Serious Treatment Emergent Adverse Event (Serious TEAE);
- Treatment-Related Serious TEAE;
- Serious TEAE Leading to Death;
- Treatment-Related Serious TEAE Leading to Death;
- Serious TEAE Leading to Treatment Discontinuation;

Statistical Analysis Plan

Sponsor Name: Bridge Biotherapeutics, Inc.
Sponsor Protocol ID: BBT401-UC-005

- Treatment-Related Serious TEAE Leading to Treatment Discontinuation

The number and percentage of subjects reporting each AE will be summarised by System Organ Class (SOC) and Preferred Term (PT) for each phase and by treatment group for the Safety Population. Tables will be sorted alphabetically by SOC. PTs will be sorted by descending overall total. The following summaries will be produced:

- TEAEs, by SOC and PT;
- Treatment-Related TEAEs, by SOC and PT;
- TEAEs by Relationship to Treatment, by SOC and PT;
- TEAEs by Maximum Severity, by SOC and PT;
- TEAEs Related to Treatment by Maximum Severity, by SOC and PT;
- TEAEs Causing Discontinuation from Treatment, by SOC and PT;
- Treatment-Related TEAEs Causing Discontinuation from Treatment, by SOC and PT;
- Serious TEAEs, by SOC and PT;
- Treatment-Related Serious TEAEs, by SOC and PT;
- TEAEs Leading to Death, by SOC and PT;

In the above summaries, subjects with more than one AE within a particular SOC are counted only once for that SOC. Similarly, subjects with more than one AE within a particular PT are counted only once for that PT. For summaries by maximum severity, subjects with multiple AEs within a particular SOC or PT will be counted under the category of their most severe AE within that SOC or PT. AEs with missing severity will be included (as severe) in the overall count of subjects with AEs, but will not be included in the counts of subjects with AEs within a SOC or PT.

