2.2 Overall Study Design

This study will comprise 2 periods: a randomised, double-blind, placebo-controlled induction phase; and a response-adaptive, double-blind extension phase.

Induction Phase

Subjects will be screened for inclusion in the study within 28 days of Day 1. Eligible subjects will be randomised in a 1:1:1 ratio; 12 subjects will receive 800 mg BBT-401-1S once daily (QD) and placebo QD, 12 subjects will receive 800 mg BBT-401-1S twice daily (BID), and 12 subjects will receive placebo BID. Subjects will receive the first dose of study drug at the study site on Day 1 and will administer study drug away from the study site for 56 days, during which they will attend 2 study site visits on Days 29 and 57. Additionally, subjects will be contacted by telephone on Day 8 for safety and compliance monitoring; however, at the discretion of the investigator, subjects may be requested to attend a study site visit on this day.

CONFIDENTIAL

Page 6 of 30

Statistical Analysis Plan

Sponsor Name: Bridge Biotherapeutics, Inc.
Sponsor Protocol ID: BBT401-UC-005

Subjects who do not agree to participate in the extension phase will attend the study site for a follow-up visit on Day 71.

Extension Phase

Subjects who complete the induction phase will be offered the opportunity to enter the extension phase after the Day 57 visit. Subjects who agree to participate in the extension phase will continue study drug administration while awaiting their clinical remission status from the local reader. Subjects will be assigned to the treatment for the extension phase treatment upon receipt of their clinical remission status.

- Subjects who achieved clinical remission in the induction phase will continue the same treatment.
- Subjects who did not achieve clinical remission in the induction phase and:
 - who received placebo BID will receive 800 mg BBT-401-1S QD and placebo QD
 - who received 800 mg BBT-401-1S QD and placebo QD will receive 800 mg BBT-401-1S BID
 - who received 800 mg BBT-401-1S BID will continue the same treatment.

Subjects will attend the study site on Days 85, 112 (last dose of treatment), and 126 (for Korean sites only). Additionally, subjects will be contacted by telephone on Day 71 for safety and compliance monitoring; however, at the discretion of the investigator, subjects may be requested to attend a study site visit on this day.

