4.2 Safety Population

The safety population will include all subjects who receive at least 1 dose of study drug. Subjects are categorized in the treatment group of the treatment they actually receive.

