6.1 General Principles

Continuous variables will be summarised by the standard descriptive statistics: number of subjects (n), mean, standard deviation, median, minimum, and maximum.

Statistical Analysis Plan

Sponsor Name: Bridge Biotherapeutics, Inc.
Sponsor Protocol ID: BBT401-UC-005

Frequency of subjects or events and percentages will be summarised in categorical variables.

All data processing, summarization and analyses will be performed using Labcorp's SAS Environment / Version 9.4 (or later) of the SAS® statistical software package.

The following principles will be applied to all TFLs unless otherwise stated:

Principle	Value	Suggested Alternative Values
Significant tests	The significance testing will be performed and the 95% confidence interval will be reported where applicable.	
Treatment group labels and order presented	
• 800 mg BBT-401-1S QD and placebo QD• 800 mg BBT-401-1S BID• Placebo BID	
• BBT-401-1S QD +Placebo QD• BBT-401-1S BID• Placebo BID
Tables	Data in summary tables presented by phase, assessment and visit (where applicable).	
Listings	All data collected presented by phase, subject, assessment and visit (where applicable), unless otherwise specified	
Descriptive summary statistics for continuous variables	Number of subjects (n), mean, standard deviation (SD), minimum, median, and maximum.	
Descriptive summary statistics for categorical variables	Frequency counts and percentages [n (%)]	
Denominator for percentages	Number of subjects in the analysis population, unless stated otherwise in table shell(s)	
Include "Missing" as category	Demographics and Other Baseline Characteristics only	
Display for 0 percentages	0	
Display to one more decimal place than collected value	Mean Mean Difference Median	
Display to two more decimal places than collected value	Standard Deviation Standard Error Confidence Interval	
Limit of precision for displays	3 decimal places for non-derived variables and 5 decimal places for derived variables	
Date Format	DDMMYYYY	

CONFIDENTIAL

Page 12 of 30

Statistical Analysis Plan

Sponsor Name: Bridge Biotherapeutics, Inc.
Sponsor Protocol ID: BBT401-UC-005

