For subjects who progress into the extension phase and have achieved clinical remission in the induction phase, subjects will continue with the same treatment in the extension phase. If subjects have not achieved clinical remission in the induction phase, then a treatment will be assigned follows the described in Section 2.2. Data display will be summarised/listed by study phase where it is applicable as subjects may switch treatments between induction phase and extension for the Safety Population.

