6.7 Safety

6.7.1 Extent of Exposure

Duration of exposure will be defined in days as:

Overall Exposure:

(date of the last dose – date of the first dose) + 1-off-drug days

If date of the first dose date is missing, then the date of the first dose dispensed will be used. If the last dose date is missing then, then the last available dose date will be used.

Induction Phase Exposure:

(date of the last dose from the induction phase – date of the first dose from the induction phase) + 1-off-drug days

If date of the first dose date is missing, then the date of the first dose dispensed in the induction phase will be used. If the last dose date is missing then, then the last available dose date in the induction phase will be used.

Statistical Analysis Plan

Sponsor Name: Bridge Biotherapeutics, Inc.
Sponsor Protocol ID: BBT401-UC-005

Extension Phase Exposure:

(date of the last dose from the extension phase – date of the first dose from the extension phase) + 1-off-drug days

If date of the first dose date is missing, then the date of the first dose dispensed in the extension phase will be used. If the last dose date is missing then, then the last available dose date in the extension phase will be used.

Duration of exposure will be listed and summarised using descriptive statistics for each phase and overall by treatment group for the Safety Population.

The number and percentage of subjects with an overall duration of exposure in the following categories will be summarised for each phase and by treatment group for the Safety Population:

- <22 days
- ≥ 22 and <57 days
- ≥ 57 days

Overall duration will be summarised by treatment received during the induction phase. Exposure during each study phase will be summarised by the actual treatment received respectively during each study phase.

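### Extension-phase adverse-event tables by regimen would not separate subjects newly escalated from QD to BID from those already on BID; summaries by treatment sequence would

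*SAP*

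**What the plan says.** On adverse events, SAP 6.7.2 says: "Summary tables of TEAEs will be produced for each phase by treatment group for the Safety Population". Events are placed in a phase by start date: "Similarly, an AE starting date which is within the extension phase will be summarised under the extension phase". The treatment-emergent definition refers only to the first dose of treatment and is not reset at a switch.

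SAP 6.7.2 does not say which treatment defines the group in the extension. Other sections point to the regimen received in that phase:

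- SAP 4.2, on the Safety Population: "Subjects are categorized in the treatment group of the treatment they actually receive".
- SAP 6.1, on why displays for that population are split by phase: "Data display will be summarised/listed by study phase where it is applicable as subjects may switch treatments between induction phase and extension for the Safety".
- SAP 6.7.1, on exposure, where the rule is explicit: "Exposure during each study phase will be summarised by the actual treatment received respectively during each study phase".
- SAP 6.5 and 6.7.1 use the induction treatment as the label only for overall, cross-phase summaries.

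The row "Treatment group labels and order presented" in SAP 6.1 lists three regimens (QD plus placebo, BID, placebo) and no sequences.

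The switching rule is in SAP 2.2 and Protocol 3.1. For remitters: "Subjects who achieved clinical remission in the induction phase will continue the same treatment". Among non-remitters, placebo subjects start QD, BID subjects stay on BID, and for the QD arm the rule is: "who received 800 mg BBT-401-1S QD and placebo QD will receive 800 mg BBT-401-1S BID". Both documents also say that subjects entering the extension keep taking study drug after the Day 57 visit until their locally read remission status arrives.

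**The concern.** A column headed BID in the extension tables would not be an arm. It would combine subjects whose daily dose has just doubled with subjects who have already taken that dose for 56 days. An event that tends to appear soon after a dose increase would be averaged over both groups, and the table would give no way to see it.

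This matters because AEs and SAEs are the primary safety endpoints (SAP 3.1) and escalation from QD to BID occurs nowhere but in the extension. Protocol 3.3 cites 1600 mg/day for 7 days in healthy subjects and 400 mg/day for up to 12 weeks in subjects with UC. With about 36 subjects and no between-group AE test, the descriptive tables carry the safety message.

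The placebo column raises a second problem. It is filled by selection on Day 57 remission, so a reader who treats it as a control is comparing subjects who are well with subjects who mostly are not.

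**Working it through.** The documents state no figure on this point, so there is none to reproduce. The column make-up follows from the switching rule.

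**Inputs.** 12 subjects per arm (SAP 2.2). Day 57 remission on placebo (p) and on QD (r) is assumed and shown as a range. Entry into the extension is assumed equal across arms.

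**Columns by regimen received, full entry:**

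- Placebo: 12p, all placebo remitters.
- QD: 12(1 − p) first-exposed placebo non-remitters, plus 12r continuing QD remitters.
- BID: 12(1 − r) escalated QD non-remitters, plus 12 continuing BID subjects.

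**BID column.** Escalated share = 12(1 − r)/[12(1 − r) + 12] = (1 − r)/(2 − r).

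| r (assumed) | Escalated | Continuing | Escalated share |
|---|---|---|---|
| 0% | 12.0 | 12 | 50% |
| 10% | 10.8 | 12 | 47% |
| 20% | 9.6 | 12 | 44% |
| 30% | 8.4 | 12 | 41% |
| 50% | 6.0 | 12 | 33% |

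If 75% of every arm enters, the shares are unchanged because the factor cancels. If a larger fraction of the QD arm than of the BID arm enters, the share can pass 50%.

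**QD column.** First-exposed share = (1 − p)/(1 − p + r). With p = r = 10% it is 0.9/1.0 = 90%. With p = 10% and r = 20% it is 0.9/1.1 = 82%. With p = 30% and r = 50% it is 0.7/1.2 = 58%. At low remission this column is mostly new starters.

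**Placebo column.** Expected size 12p, chance of no remitter (1 − p)^12, and chance of at most two from the binomial:

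| p (assumed) | Expected | None | At most 2 |
|---|---|---|---|
| 5% | 0.6 | 54% | 98% |
| 10% | 1.2 | 28% | 89% |
| 20% | 2.4 | 7% | 56% |

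With 0 events in 2 subjects, the exact 95% upper limit is 1 − 0.025^(1/2) = 84%.

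**What pooling does to a displayed rate.** Displayed BID rate = s·e + (1 − s)·c, where s is the escalated share, e the event risk after escalation and c the risk in continuing subjects. At s = 44.4% (r = 20%), with assumed risks:

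- e = 30%, c = 5%: 13.3 + 2.8 = 16.1%
- e = 30%, c = 10%: 13.3 + 5.6 = 18.9%
- e = 30%, c = 20%: 13.3 + 11.1 = 24.4%
- e = c: no distortion
- e = 10%, c = 30%: 4.4 + 16.7 = 21.1%, which overstates the escalated group's risk

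**Alternative reading.** If treatment group means induction arm, the BID column is clean. The placebo column then mixes placebo-placebo with placebo-QD (at p = 10%, 1.2 and 10.8 subjects, so 90% of it is on drug), and the QD column mixes QD-QD with QD-BID.

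**The case against.** Several points on the other side stand.

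The grouping rule is inferred. The explicit sentence on treatment received in each phase concerns exposure, the table shells are not visible, and text after the treatment-group wording in SAP 6.2 is redacted. But the inference is the natural one, and the induction-arm reading also mixes sequences.

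A reader might infer that the plan cannot show the effect of starting the drug. The documents do not support that. The induction tables describe first exposure to both regimens against concurrent randomised placebo, and the extension QD column is mostly new starters when remission is low.

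A reader might also infer that the BID column would show about half the true rate after escalation. That follows only from assumed risks such as 30% and 5%. The documents give no event rates and do not establish an early excess after escalation. Protocol 3.3 reports plasma levels below quantification at up to 1600 mg/day, although that does not rule out local gut effects.

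Nor do the documents show that the placebo column inflates a drug excess. The AE tables are descriptive, no between-group AE test is planned, and a column of one or two subjects is a poor candidate for a control. Fewer UC-related events in remitters is plausible but undocumented. It is also not strictly true that only remitters take placebo in the extension, because placebo non-remitters may do so while awaiting the local read.

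Finally, all AEs are listed by phase and subject, and SAP 6.2 reports the treatment received in the extension, so a reader could trace sequences by hand. That reduces the harm but does not supply a planned summary.

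**Conclusion.** The point holds as a limitation of presentation. On the natural reading of the SAP, the extension BID column pools newly escalated with continuing subjects. The escalated share is 41% to 47% for assumed QD remission of 30% down to 10%, and at most 50% with equal entry per arm. Events after escalation are therefore not isolated in any visible planned summary. The mixing follows from the switching rule and needs no assumption about event rates; the size and direction of any distortion do. The QD column has the same defect to a lesser degree. The placebo column, about 0 to 3 subjects at an assumed 5% to 20% remission, should not be read as a comparator. None of this affects the randomised induction comparison.

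**What to change.** In SAP 6.7.2, and for extension exposure in SAP 6.7.1:

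- Add extension-phase summaries by sequence: placebo-placebo, placebo-QD, QD-QD, QD-BID and BID-BID, each with its own number treated. Keep the regimen columns as totals.
- Assign events by onset relative to the first dose of the assigned extension regimen. Events during the wait for remission status then stay with the induction regimen. The visible SAP does not define this boundary.
- State that the sequence groups are selected on Day 57 remission, that the display is descriptive, and that placebo-placebo is not a control. QD-BID describes subjects who were escalated; it does not estimate the effect of escalating, because they are all non-remitters observed later in time.

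The cost is SAP wording and table columns, with no new data and no change to treatment. Some columns will be very small: with 10% remission in each arm and full entry, the expected numbers are 1.2, 10.8, 1.2, 10.8 and 12, so counts should be shown alongside any percentage.

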3. INVESTIGATIONAL PLAN

3.1. Overall Study Design and Plan

This study will comprise 2 periods: a randomised, double-blind, placebo-controlled induction phase; and a response-adaptive, double-blind extension phase.

Induction Phase

Subjects will be screened for inclusion in the study within 28 days of Day 1.

Eligible subjects will be randomised in a 1:1:1 ratio; 12 subjects will receive 800 mg BBT-401-1S once daily (QD) and placebo QD, 12 subjects will receive 800 mg BBT-401-1S twice daily (BID), and 12 subjects will receive placebo BID. Subjects will receive the first dose of study drug at the study site on Day 1 and will administer study drug away from the study site for 56 days, during which they will attend 2 study site visits on Days 29 and 57. Additionally, subjects will be contacted by telephone on Day 8 for safety and compliance monitoring; however, at the discretion of the investigator, subjects may be requested to attend a study site visit on this day.

Subjects who do not agree to participate in the extension phase will attend the study site for a follow-up visit on Day 71.

Extension Phase

[figure not shown]
Subjects who complete the induction phase will be offered the opportunity to enter the extension phase after the Day 57 visit. Subjects who agree to participate in the extension phase will continue study drug administration while awaiting their clinical remission status from the local reader. Subjects will be assigned to the treatment for the extension phase treatment upon receipt of their clinical remission status.

- Subjects who achieved clinical remission in the induction phase will continue the same treatment.
- Subjects who did not achieve clinical remission in the induction phase and:
 - who received placebo BID will receive 800 mg BBT-401-1S QD and placebo QD
 - who received 800 mg BBT-401-1S QD and placebo QD will receive 800 mg BBT-401-1S BID
 - who received 800 mg BBT-401-1S BID will continue the same treatment.

Subjects will attend the study site on Days 85 and 112 (follow-up visit). Additionally, subjects will be contacted by telephone on Day 71 for safety and compliance monitoring; however, at the discretion of the investigator, subjects may be requested to attend a study site visit on this day.

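### Unless the CRF records worsening as a new event, adverse events that worsen after the extension switch stay under the induction treatment; the extension start for AE allocation is also undefined

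*SAP*

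**What the plan says.** SAP 3.1 names adverse events and serious adverse events as the primary safety endpoints. SAP 6.7.2 sets the layout: "Summary tables of TEAEs will be produced for each phase by treatment group for the Safety Population". Phase is then decided by onset: "AE starting date which is within the induction phase will be summarised under the induction phase". The same section gives the counterpart for the later phase: "Similarly, an AE starting date which is within the extension phase will be summarised under the extension phase". The tables made for each phase include maximum severity, serious events and events causing discontinuation.

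An event is treatment-emergent if it begins at or after the first dose. The definition also admits an event that began "prior to the date and time of the first dose of treatment whose severity worsens" from that dose on. It has no counterpart for the first dose of a new treatment in the extension.

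Treatment group comes from other sections. SAP 4.2 states: "Subjects are categorized in the treatment group of the treatment they actually receive". SAP 6.1 splits displays by phase because subjects may change treatment, and SAP 6.7.1 reports exposure in each phase by the treatment actually received in it.

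On timing, SAP 2.2 says: "Subjects who complete the induction phase will be offered the opportunity to enter the extension phase after the Day 57 visit". Protocol 3.1 adds: "Subjects who agree to participate in the extension phase will continue study drug administration while awaiting their clinical remission status from the local reader". The new treatment comes later: "Subjects will be assigned to the treatment for the extension phase treatment upon receipt of their clinical remission status" (SAP 2.2). Neither document gives a date or time at which the extension begins for allocating adverse events.

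**The concern.** Two gaps follow from these rules.

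The first is worsening. The SAP accepts that an event which worsens once treatment has begun belongs to that treatment, but applies this only at Day 1. Placebo subjects not in remission first take active drug in the extension, and QD subjects not in remission first take BID there. An event that was mild in induction and became severe after the switch keeps its induction start date, so it stays in the induction column. The maximum-severity, serious and discontinuation tables follow the same phase rule. Severity reached on active drug could therefore appear under placebo, in the column that serves as the randomised comparator.

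The second is the phase boundary. Between the Day 57 visit and the arrival of the remission status, the subject is still on induction treatment. If programming starts the extension at Day 57, an event in that interval is shown under a treatment, or for QD-to-BID subjects a dose level, that has not been started.

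**Working it through.** **1. Worsening after the switch.** Take a subject who moves from placebo to QD and apply SAP 6.7.2 as written.

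| Event history | Where it is tabulated | Assessment |
|---|---|---|
| Starts on placebo, does not worsen | Induction, placebo | Correct |
| Starts on placebo, worsens after the first QD dose, one AE record | Induction, placebo only | Onset correct; later severity charged to placebo; nothing under extension QD |
| Same, but worsening entered as a new AE record | Induction, placebo, and extension, QD | Correct |
| Starts after the first QD dose | Extension, QD | Correct |

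The second row is the problem, and it does not depend on where the phase boundary lies. Whether the second or third row applies depends on CRF practice. Protocol Appendix 4 refers to eCRF completion instructions, but neither document gives the rule. The TEAE definition speaks of an event with a start before dosing whose severity later increases. That suggests a worsened event keeps its first start date, but does not settle the matter.

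Separately, a completely missing start date is imputed to the first study dose (SAP 6.7.2), which also places the event in induction.

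**2. Where the extension starts.** The only stated figure bearing on this is the total duration of about 20 weeks for extension subjects (Protocol 3.1).

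- Screening 28 days plus 112 days: (28 + 112)/7 = 20.0 weeks, which reproduces it.
- Day 57 to Day 112: 55 days, 55/7 = 7.9 weeks, matching the stated extension of about 8 weeks.
- 4 + 8 + 8 = 20 weeks fits an extension starting at about Day 57.
- The synopsis gives induction as about 10 weeks. That fits only if the Day 71 follow-up is included (71/7 = 10.1), and 4 + 10 + 8 = 22.

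The durations lean towards Day 57 but are approximate and do not fix an analysis boundary. There are three possible readings for an event during the wait:

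- Extension starts at Day 57: the event is shown under the new treatment, which has not been taken.
- Induction runs until the first newly assigned dose: the event is shown correctly.
- Induction ends at Day 57 and the extension starts at the first newly assigned dose: the event belongs to no phase.

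**3. Number of subjects who could be affected.** Arms are 12 each (SAP 2.2). Only the placebo and QD arms can change treatment: 12 + 12 = 24 of 36. This is a ceiling.

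- Assumed 20% remission, everyone enters: 24 × 0.8 = 19.2.
- Assumed 20% remission and 30% not entering: 24 × 0.7 × 0.8 = 13.4.

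These count switchers, not misplaced events. The documents give no event rate.

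**4. Weight of one misplaced subject.**

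- 12-subject column: 1/12 = 8.3 percentage points. Exact 95% intervals: 0/12 gives 0 to 26.5%; 1/12 gives 0.2 to 38.5%.
- With full entry and no remission, the extension BID column holds 12 + 12 = 24, so 1/24 = 4.2 points.

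**5. Length of the wait, under the Day 57 reading only.** The documents do not state it, so these are assumptions, with all 12 placebo subjects switching and 12 × 55 = 660 extension person-days.

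| Assumed wait | Placebo person-days shown under QD | Share of 660 |
|---|---|---|
| 3 days | 12 × 3 = 36 | 5% |
| 7 days | 12 × 7 = 84 | 13% |
| 14 days | 12 × 14 = 168 | 25% |

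The wait could also be nil: the local read decides assignment (Protocol 7.1.1), and the endoscopy may be done up to 7 days before the Day 57 visit (Protocol Appendix 11).

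**The case against.** The strongest reply is that the SAP is less crude than the start-date rule suggests. A reader might infer that both phase and treatment are fixed by start date alone. They are not: start date picks the phase, and treatment follows from SAP 4.2, 6.1 and 6.7.1. Section 6.7.1 also refers to the first dose from the extension phase, so a dose-based boundary is a natural reading. That stands as a reading, but 6.7.1 does not say whether a dose taken during the wait counts, and 6.7.2 does not refer to it.

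A reader might also infer that events in the wait distort the randomised comparison of drug with placebo. The documents do not support this. Under the Day 57 reading those events fall outside induction, and in the extension only placebo remitters stay on placebo, so there is no randomised placebo contrast there.

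On worsening, the event did begin on placebo, so its place in the placebo incidence table is right. What is wrong is the severity attached to it and its absence from the extension. If the CRF opens a new record when an event worsens, even that disappears.

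Finally, safety analysis is descriptive (Protocol 8.5). All events are listed with a treatment-emergence flag, and serious events, deaths and discontinuations have their own listings. In about 36 subjects each case can be checked against dosing dates. This limits the harm, but the listings do not correct the summary tables.

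**Conclusion.** The concern holds within limits. The worsening gap is the firmer part: it follows from the stated TEAE definition and phase rule, and needs only the assumption that worsening is not entered as a new adverse event. The boundary gap is an omission that becomes an error only under some readings. It is not established that events in the wait will be misplaced.

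The exposed group is at most 24 of 36 subjects. It would be wrong to infer that all placebo and QD subjects not in remission will switch, because entry requires completing induction and agreeing to continue. One misplaced subject is 8.3 points in a 12-subject column and less in a larger extension column. Efficacy results are not affected, and the induction incidence counts by onset are sound. The exposure lies in the severity, serious and discontinuation tables for induction, and in the extension tables generally. Because adverse events are the primary safety endpoint, the SAP should be amended.

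**What to change.** In SAP 6.7.2:

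1. Set the boundary for adverse event allocation at the date and time of the first dose of extension-assigned treatment, and state that doses taken while awaiting remission status belong to induction.
2. Assign each event to the treatment being taken at its onset.
3. Define an extension TEAE as an event that starts, or increases in severity, on or after that dose.
4. In the induction maximum-severity tables, count only the severity reached before that dose, where the date of the severity change is recorded.
5. State whether the CRF records worsening as a new event or as a change to the existing one, so that items 3 and 4 are programmed accordingly.

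The cost is SAP wording and modest programming. SAP 6.7.1 already needs the first dose date in the extension, and treatment, visits and procedures do not change. Item 4 can be applied only where severity changes are dated. A worsened event may appear in both phases, which a table footnote can explain.
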